6.2.3 Analysis of other exploratory efficacy variables

Other exploratory efficacy variables will be as follows:

- Time to onset of kidney failure
- Time to onset of ESRD
- Time to onset of eGFR decrease to less than 15 mL/min/1.73 m² sustained over at least 4 weeks

- Time to onset of eGFR decrease of $\geq 40\%$ sustained over at least 4 weeks
- Time to onset of eGFR decrease of $\geq 57\%$ sustained over at least 4 weeks
- Time to CV death
- Time to non-CV, non-renal death
- Time to first CV hospitalization (either hospitalization for HF, other cardiovascular hospitalization or adjudicated CV event associated with hospitalization)
 - Causes for other cardiovascular hospitalizations include unstable angina, arrhythmia, and peripheral arterial disease.
 - CV events associated with hospitalization include (if not already considered as “other cardiovascular hospitalization”) CV death, new onset of atrial fibrillation/flutter, non-fatal myocardial infarction, non-fatal stroke and transient ischemic attack.
- Time to first hospitalization for HF
- Time to first non-fatal stroke
- Time to first non-fatal myocardial infarction
- Time to stroke (fatal or non-fatal)
- Time to myocardial infarction (fatal or non-fatal)
- Time to first occurrence of the composite endpoint of CV death for HF or HF hospitalization
- Time to first occurrence of the composite endpoint of CV death, hospitalization for HF or non-fatal myocardial infarction
- Time to first occurrence of the composite endpoint of CV death, non-fatal stroke or non-fatal myocardial infarction
- Time to first occurrence of the composite endpoint of CV death or hospitalization for HF
- Time to first occurrence of the composite endpoint of CV death, kidney failure, eGFR decrease of $\geq 57\%$ sustained over at least 4 weeks or renal death
- Number of subjects with new diagnosis of atrial fibrillation or atrial flutter
- Number of subjects with new diagnosis of HF
- Change in UACR from baseline
- Change in eGFR from baseline
- Regression from very high to high albuminuria and high albuminuria to normal albuminuria accompanied by a decrease in UACR of at least 30% from baseline
- Number of subjects with UACR decrease of at least 30% from baseline at any time post-baseline

- Number of subjects with UACR decrease of at least 50% from baseline at any time post-baseline
- Change in QoL summary scores measured by the following health-related quality of life (HRQoL) questionnaires: Kidney Disease Quality of Life (KDQOL 36) and EuroQol Group 5 dimension, 5 level questionnaire (EQ 5D 5L)

All these other efficacy variables will be analyzed in FAS and PPS (as applicable) in an explorative manner. For all PPS analyses, only data points and events up to 30 days after stop of study drug will be considered.

6.2.3.1 Components of primary and secondary composite endpoints

Consistent with the methods for the primary and secondary efficacy variables, components or composites of the components of the primary and secondary time-to-event endpoints (as included in the list of other exploratory efficacy variables above) will be analyzed as exploratory time-to-event variables using the stratified logrank test stratified by the stratification factors. A point estimate of the hazard ratio and a corresponding two-sided 95% confidence interval will be calculated using a stratified Cox proportional hazard regression model. Kaplan Meier curves will be provided for the cumulative proportions of events by treatment groups.

6.2.3.2 UACR and albuminuria

UACR during the study will be summarized descriptively by treatment group and visit including ratios to baseline. These analyses will be performed overall and separated by the stratification factors (region, type of albuminuria at screening, eGFR category at screening, history of CVD).

The log-transformed ratio of UACR to baseline at each visit up to the last visit with a reasonable number of subjects with UACR measurements will be analyzed by a mixed model repeated measures (MMRM) with the factors treatment group, visit, treatment-by-visit interaction, factors for the stratification levels, log-transformed baseline value as covariate nested within type of albuminuria and log-transformed baseline value by visit interaction. Pairwise ratios between the finerenone and the placebo treatment group will be calculated and corresponding two-sided 95% confidence intervals will be computed.

An on-treatment analysis including measurements restricted to up to 30 days after last intake of study drug will be performed using the same model as above.

The SAS procedure PROC MIXED will be used estimating covariance patterns within subjects to adjust for the within subject variance. For each treatment group a separate covariance pattern will be estimated based on an unstructured covariance. In case of convergency issues, an alternative covariance matrix will be used, with Toeplitz matrix as first choice alternative.

Frequency tables will be generated for the number of subjects with a relative decrease and increase in UACR of $\geq 30\%$, $\geq 40\%$ and $\geq 50\%$ from baseline UACR. The analysis will be performed for each visit and for any time post baseline. The analysis will also be performed stratified for each level of the stratification factors.

A shift table will be provided displaying the number of subjects who changed from baseline to each visit from very high albuminuria to high albuminuria, from very high albuminuria to normalalbuminuria (UACR <30mg/g), from high albuminuria to normalalbuminuria (UACR <30mg/g), from high albuminuria to very high albuminuria and from normalalbuminuria (UACR <30mg/g) to high and very high albuminuria by treatment group and overall. The albuminuria category changes will only be considered as shifts, if they are accompanied by a UACR decrease or increase of at least 30% from baseline to the respective visit.

The additional categorical UACR efficacy variables will be summarized for presence or absence of the event using logistic regression with the factors treatment group and stratification levels. Pairwise differences between the finerenone and the placebo treatment group will be calculated and corresponding two-sided 95% confidence intervals will be computed.

6.2.3.3 Decrease in eGFR

eGFR will be summarized descriptively by treatment group and visit including absolute and relative changes to baseline. These analyses will be performed overall and separated by the stratification factors.

The absolute change of eGFR to baseline at each visit up to the last visit with a reasonable number of subjects with eGFR measurements will be analyzed by a mixed model with the factors treatment group, visit, treatment-by-visit interaction, factors for the stratification levels, baseline value as covariate (nested within eGFR category) and baseline by visit interaction. Pairwise differences between the finerenone and the placebo treatment group will be calculated and corresponding two-sided 95% confidence intervals will be computed.

An on-treatment analysis including measurements restricted to up to 30 days after last intake of study drug will be performed using the same model as above.

The SAS Procedure PROC MIXED will be used estimating covariance patterns within subjects to adjust for the within subject variance. For each treatment group a separate covariance pattern will be estimated based on an unstructured covariance. In case of convergency issues, an alternative covariance matrix will be used, with Toeplitz matrix as first choice alternative.

Frequency tables will be generated for the number of subjects with a relative decrease in eGFR of $\geq 30\%$, $\geq 40\%$, $\geq 50\%$ and $\geq 57\%$ from baseline eGFR. The analysis will be performed for each visit and for any time post baseline.

For each patient with 1 or more post-baseline eGFR measurements, the annualized change in eGFR will be calculated by fitting the patient's eGFR assessments into a linear regression model with time in years as the independent variable. The derived annualized change will be analyzed using an ANCOVA model including baseline, treatment group and stratification factors as fixed-effects.

The following additional analysis of eGFR slopes (calculated as annualized change from one visit to another) will be performed:

- Total eGFR slope from baseline (Visit 1) to the PD or EOS Visit

- Acute eGFR slope from baseline to Month 4
- Chronic eGFR slope from Month 4 to the PD or EOS Visit

An ANCOVA model will be fitted to the eGFR efficacy variables including the factors treatment group, the stratification factors and the baseline eGFR as covariate. Corresponding two-sided 95% confidence intervals will be computed. In addition, correlation analyses between short-term eGFR changes between baseline and Month 4 after randomization (acute slope), and long-term eGFR decline (chronic slope) will be performed overall and by treatment group.

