An ANCOVA model will be fitted to the GFR efficacy variables including the factors treatment group, the stratification factors (type of albuminuria, eGFR category, history of CVD) and the baseline GFR as covariate. Corresponding two-sided 95% confidence intervals will be computed. In addition, correlation analyses between short term GFR changes between Visit 1 (baseline) and Visit 3 (Month 4) after randomization, and long term GFR decline (chronic slope).

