4.5.3 Other data handling

Only the data provided by the central laboratory will be used for analysis, values from local laboratories will not be used in the statistical analysis and will be listed only unless there are no values from the central laboratory available for baseline.

In case of retests for Run-in and Screening visits, the closest measurement prior to randomization will be used for analysis instead of the scheduled measurements. At all visits starting at Visit 1 and if not stated otherwise, only the values at scheduled measurements will

be used for analysis. In the unexpected case that more values than planned are available for a scheduled visit, only the first valid value will be used.

For the derived visit “Any time post-baseline” (applicable for efficacy) this will include any measurement after date of randomization, including unscheduled assessments. For the derived visit “Any treatment-emergent” (applicable for safety), only assessments on or after study medication start date until 3 days after the date of any temporary or permanent interruption of study drug, including unscheduled assessments, will be considered.

For those laboratory values which are <LLOQ (Lower limit of quantification), half the value of the LLOQ will be used for analysis. Differences between 2 values <LLOQ will be assigned values of 0. Ratios between 2 values <LLOQ will be assigned a value of 1. For values which are >ULOQ (Upper limit of quantification), the ULOQ will be used for analysis. This rule does not apply to the finerenone plasma concentration data.

In case of log-normally distributed data, descriptive statistics other than minimum, maximum and median will only be calculated if at least 2/3 of the individual data were measured and were above the lower limit of quantification. In tables showing descriptive statistics, where values below LLOQ are included, these descriptive statistics will be marked.

Urinalysis is assessed 3 times per visit. UACR will be determined 3 times at each visit from first morning void urine samples collected on 3 consecutive days. For the analyses of UACR, the 3 measurements at one visit will be combined provided that at least 2 measurements are available. First, the coefficient of variation (CV) will be calculated for the 3 values as follows considering the log-normal distribution for UACR [7]:

$$CV = \sqrt{\exp(SD_{\ln}^2) - 1},$$

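### The acute and chronic eGFR slopes that the SAP correlates share one Month 4 value, so visit-to-visit variation biases the correlation in the negative direction

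*SAP*

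**What the plan says.** SAP 6.2.3.3 introduces "eGFR slopes (calculated as annualized change from one visit to another") and lists, among others, "Acute eGFR slope from baseline to Month 4" and "Chronic eGFR slope from Month 4 to the PD or EOS Visit". An ANCOVA compares the slopes between arms. The same section then plans "correlation analyses between short-term eGFR changes between baseline and Month 4 after randomization (acute slope), and long-term eGFR decline (chronic slope"), which "will be performed overall and by treatment group".

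Under SAP 4.5.3, visits from Visit 1 onwards contribute scheduled values only. If a visit has more values than planned, "only the first valid value will be used". There is therefore one Month 4 eGFR per patient, and it serves both slopes.

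The status is plain from SAP 6.2.3: "All these other efficacy variables will be analyzed in FAS and PPS (as applicable) in an explorative manner". No correlation coefficient, test or interpretation is specified.

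Protocol 9.7.8.1.3 plans the same kind of analysis for measured GFR in the iohexol sub-study. It correlates the change from Visit 1 to Visit 3 with "long term GFR decline (chronic slope"), where the chronic slope runs from Visit 3.

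**The concern.** Write B, M and E for the baseline, Month 4 and final (PD or EOS) eGFR. The acute quantity is proportional to M - B and the chronic slope to E - M. If M happens to read low, the dip looks larger and the later loss looks smaller in the same patient. This is mathematical coupling and needs no biology.

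The question behind the analysis is whether the early fall in eGFR says anything about the later course of kidney function. A correlation with a built-in negative component cannot answer it as it stands, because the reader cannot tell how much is coupling and how much is a real relation. Repeating it by arm does not help: the coupling is within the patient and is present in both arms. The baseline covariate in the ANCOVA belongs to a separate analysis and does not remove the error in M. Neither document separates the two measurements or corrects for the shared error.

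**Working it through.** **No figure to reproduce.** The documents state no visit-error SD, slope SD or expected correlation.

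**Inputs from the documents**
- Definitions of the two slopes: SAP 6.2.3.3. Month 4 is taken as 1/3 year.
- Planned follow-up: 44 to 48 months in total, with 11 or 7 months for the last patient recruited (SAP 3, Protocol 10.4). I spread individual follow-up uniformly over 11-44 and 7-48 months, and also ran a fixed 36 months.
- Later calendar: first randomization October 2015, last January 2019 (SAP 6.2.4), SAP 6.0 dated February 2021. If the trial ended around the start of 2021 (an assumption), follow-up is nearer 24-63 months.
- Number randomized: about 7400 (SAP 3).

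**Inputs assumed**
- Independent visit errors, SD σ = 3, 5 or 7 mL/min/1.73m².
- SD of the true acute change, τa = 0, 3 or 5.
- SD of the true chronic slope, τc = 2 or 4 per year, around a mean of -3 per year.
- No true relation between acute change and chronic slope.

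**Formula.** Let L be the time in years from Month 4 to the last value. Dividing the acute change by the constant 1/3 year does not alter a correlation. Then

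Cov(M - B, (E - M)/L) = -σ²/L

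r = -(σ²/L) / √[(2σ² + τa²)(2σ²/L² + τc²)]

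The numerator is always negative. With noise only (τa = τc = 0) and a common L, r = -σ²/√(2σ² × 2σ²) = -0.50, whatever σ is.

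**Numbers for 36 months of follow-up (L = 32/12 = 2.667)**
- σ = 3, τa = 5, τc = 4: -3.375/√(43 × 18.53) = -0.12
- σ = 5, τa = 5, τc = 4: -9.375/√(75 × 23.03) = -0.23
- σ = 7, τa = 3, τc = 2: -18.375/√(107 × 17.78) = -0.42

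**Simulation, 400,000 patients per setting, true correlation 0.** Lowest and highest r over all combinations of σ, τa and τc:

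| Follow-up (months) | Planned definition |
|---|---|
| fixed 36 | -0.44 to -0.12 |
| 11-44 | -0.42 to -0.17 |
| 7-48 | -0.37 to -0.18 |
| 24-63 | -0.41 to -0.11 |

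As an illustration, take σ = 5, τa = 3, τc = 2 and 11-44 months. Here r = -0.38, and the rank correlation is the same. The median chronic slope is -1.1 per year in the third of patients with the largest dip and -4.9 in the third with the smallest dip, although the true slope distribution is identical in both.

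**Regression instead of two points.** If the chronic slope is a line fitted to 4-monthly values that include Month 4, r is still -0.07 to -0.36 across the settings examined.

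**Chronic slope from Month 8.** With no shared value, |r| is at most 0.005 in every setting, which is simulation error.

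**Adding each patient's own decline.** If the chronic slope already runs during the first 4 months, slope × 1/3 year is part of M - B and pushes r upwards. The planned correlation then runs from -0.41 to +0.12, and the Month 8 version from about +0.01 to +0.27.

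**Scale.** The two-sided 5% threshold is |r| ≈ 1.96/√7400 = 0.023 overall and 1.96/√3700 = 0.032 per arm, if nearly all patients contribute. A spurious r of -0.1 is well outside both.

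**The case against.** *The result depends on the truth as well as on noise.* This stands. A reader might infer that the analysis will report a larger dip with slower loss whatever the truth. The documents do not support that. The observed correlation also contains any real relation, and ongoing decline in the first 4 months works in the opposite direction; in some settings above it cancels or outweighs the bias. The direction of the bias is known, given independent errors, but the sign of the result is not.

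*The size rests on assumed variances.* Also true. Positive correlation between visit errors would shrink it, and so does longer follow-up when true slopes vary substantially. The 24-63 month row shows that the bias does not then disappear.

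*The slope may not be two-point.* The preceding paragraph of SAP 6.2.3.3 fits a regression for the annualized change, so a regression within the window is a possible reading. It reduces the bias but does not remove it.

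*The placebo arm is a benchmark.* Only partly: it carries the same coupling, but the comparison does not recover the correlation within either arm.

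*It is exploratory.* Correct. It lies outside the testing hierarchy in SAP 4.7, and no test of the correlation is planned. That limits the weight of the point, but an exploratory analysis should still be able to address its own question.

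*The sponsor has already considered such analyses.* SAP 7.1 (Modification 15) removed an analysis relating UACR change to Month 4 with later events, because confounding with treatment could not be excluded. SAP 7.4 added the by-arm repeat here. Analysing by arm deals with confounding by treatment, not with a shared measurement.

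**Conclusion.** The point holds as a bias of known direction in one exploratory analysis. Because the Month 4 eGFR closes the acute interval and opens the chronic one, its visit-to-visit variation pulls the planned correlation downwards, overall and in each arm. With independent visit errors of SD 3-7, true acute-change SD 0-5, true slope SD 2-4 per year and no true relation, the spurious part is roughly -0.1 to -0.4. None of these variances is in the documents. The raw correlation cannot be read at face value in either direction.

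Two wider inferences are not supported. The between-arm slope comparisons do not correlate the two slopes and are not affected by this coupling, and no primary or secondary test is touched. The iohexol sub-study has the same structure through its shared Visit 3 value, but Protocol 9.7.8.1.3 foresees at least 50 subjects per study, so the argument that even a small spurious value would look nominally significant in thousands of patients does not carry over. That sub-study is reported separately (Protocol 9.7.8.1, SAP 7.3).

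**What to change.** For this correlation only, amend SAP 6.2.3.3 in one of two ways.

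1. Keep the acute change as baseline to Month 4 and compute the chronic slope from Month 8 onwards, so that the two share no measurement. Visit 4 already includes central chemistry (Protocol Table 9-1 and 9.2.6). State the minimum follow-up required after Month 8.
2. Fit one joint mixed model with correlated patient-level acute and chronic effects and a residual error term, and report the model-based correlation.

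The SAP should add that option 1 removes the shared-error bias but does not separate the acute response from decline already under way; a modest positive correlation could still reflect that decline. If the planned version is retained as well, label it as biased in the negative direction.

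Leave the between-arm slope analyses unchanged. The separate iohexol analysis should follow the same principle; its next scheduled measurement after Visit 3 is Visit 5, Month 12 (Protocol Table 9-2).

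The cost is a change of SAP wording and one derivation, with no new data. Patients with little or no follow-up beyond Month 8, including those whose PD visit comes earlier, drop out of this exploratory analysis.

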6.2.3.4 Health-related quality of life

The KDQOL-36 will be used. The items of the KDQOL 36 are grouped as follows:

- Items 1-12: Physical Component Summary (PCS) / SF-12 physical health composite on physical functioning, role-physical, bodily pain, general health, vitality, social functioning, role-emotional, mental health
- Items 1-12: Mental Component Summary (MCS) / SF-12 mental health composite on physical functioning, role-physical, bodily pain, general health, vitality, social functioning, role-emotional, mental health (including a different weighting than the PCS)
- Items 13-16: Burden of Kidney Disease; interference with daily life, time to deal with kidney disease, frustration, feeling like a burden
- Items 17-27: Symptoms / Problems; general health, activity limits, ability to accomplish desired tasks, depression/anxiety, energy level, social activities (item 28 concerning dialysis will be only collected in patients on dialysis)
- Items 29-36: Effects of Kidney Disease; impact of fluid & diet limits, ability to work around the house and to travel, feeling depending on medical team, stress or worries, sex life, personal appearance

Domain scores for each of the 5 domains (Physical Component Summary, Mental Component Summary, Burden of Kidney Disease, Symptoms / Problems, and Effects of Kidney Disease) will be calculated according to the KDQOL scoring instruction (see reference 1). The KDQOL-36 domain scores will be presented by visit and treatment group by means of number of observations, number of missing values, minimum, first quartile, mean, SD, median, third quartile, and maximum, including the changes from baseline. In addition to the analysis of the KDQOL-36 for the overall population, this will be repeated for patients with or without ESRD at any point during the study.

The absolute change of the PRO to baseline at each visit up to the last visit with a reasonable number of subjects with PRO measurements will be analyzed by a mixed model with the factors treatment group, visit, treatment by visit interaction, factors for the stratification levels, baseline value as covariate and baseline by visit interaction. Pairwise differences between the finerenone and the placebo treatment group will be calculated and corresponding two-sided 95% confidence intervals will be computed.

The SAS Procedure PROC MIXED will be used estimating covariance patterns within subjects to adjust for the within subject variance. For each treatment group a separate covariance pattern will be estimated based on an unstructured covariance. In case of convergency issues, an alternative covariance matrix will be used, with Toeplitz matrix as first choice alternative.

For the EQ-5D-5L, summary scores will be calculated out of the 5 dimensions according to the scoring instructions from Europe (UK as a representative country within Europe) and the US (see reference 2) and to the EQ-5D-5L Value Sets (see reference 3). The values and the changes from baseline of the summary scores and the EQ Visual Analogue scale (VAS) will be summarized by treatment group and visit using the same descriptive statistics as for KDQOL.

The EQ-5D-5L will be analyzed similarly to the KDQOL-36.

6.2.3.5 New diagnosis of atrial fibrillation, new diagnosis of heart failure and regression of albuminuria

These other exploratory efficacy variables will be summarized for presence or absence of the event using logistic regression with the factors treatment group and stratification levels (region, type of albuminuria, eGFR category and history of CVD). Pairwise differences between the finerenone and the placebo treatment group will be calculated and corresponding two-sided 95% confidence intervals will be computed.

